integrated from select national VA data sources. VINCI servers for data, applications and virtual sessions are physically located at the VA Austin Information Technology Center (AITC), located in Austin, Texas. This secure enclave with 105 high-performance servers and 1.5 petabytes of high-speed data storage has multiple layers of security and disaster recovery to prevent data loss.

To ensure the protection of Veteran data, VINCI maintains compliance with the guidelines set forth by Veterans Health Administration (VHA) Handbook 1200.12, Use of Data and Data Repositories in VHA Research, and all other applicable VA and VHA policies and regulations. In addition, VINCI has undergone all security certification activities in support of obtaining an Authorization to Operate (ATO). Access to VINCI resources are approved in accordance with the requirements of National Data Systems (NDS), VHA Handbook 1200.12, Use of Data and Data Repositories in VHA Research, and all other applicable VA and VHA policies and regulations. All data transferred from VINCI is subject to audit for compliance.

VA-credentialed research or operations staff are granted access to study-specific data along with tools for analysis and reporting in the secure, virtual working environment through a certified VHA network computer within the VA. If not working within a VA or VHA hosted office environment containing VA network access, researchers may apply for and then access VINCI through an approved Virtual Private Network (VPN) and Remote Desktop application. The remote computing environment enables data analysis to be performed directly on VINCI servers, offering several advantages: uniform security standards for access; a common point of entry for all investigators who use the data; tools for analysis and reporting; tighter and more consistent control of data quality; and the ability to standardize and update terminology and format as technology and methodology improve.

*Storage of Study Data.* VINCI will be used only to assist in data analysis; data will not be obtained through VINCI. All study data will be stored in password-protected database stored on the VAPORHCS R01PORHSM03 Server. For data uploaded to VINCI for data analysis, the data will be kept in accordance with the Department of Veterans Affairs Record Control Schedule 10-1 (RCS 10-1). Storage and transfer of any Personally Identifiable Information (PII) or Protected Health Information (PHI) must be done in accordance with applicable VA and VHA policies and directives, state and federal regulations, and applicable statutes including the Health Insurance Portability and Accountability ACT (HIPAA). Unless explicitly requested and approved by data stewards, all sensitive patient data must remain on VINCI project servers and only aggregate data without PII / PHI may be transferred from VINCI. Any desired change in data storage location or transfer requires amending the original data request with an updated of disposition of study data. The amendment must be approved by all data stewards before data may be transferred.

Violations of data policy or approved use of data will be subject to full penalty of law, which may include suspension of access privileges, reprimand, suspension from work, demotion, removal, and criminal and civil penalties.

Upon completion of the research project, the study principal investigator in conjunction with the VA Information Security Officer (ISO), and in accordance with VA policy, will ensure that, study data containing sensitive, confidential information will be returned to the VA, sanitized and removed from all servers, desktops, removable storage devices, etc.

*Data Access - VINCI.* Only study team personnel explicitly authorized by data stewards will have access to project data. The study principal investigator has the responsibility for security of study. VINCI data managers and VA OI&T personnel not under the purview of the study principal investigator control the servers, network, processors, firewall and software in the VINCI environment, including access rights granted to study personnel.

When study personnel are no longer part of the research team, the study principal investigator will amend the data access request to terminate that person's access to all study data and notify the VA Information Security Officer of such action. No sensitive patient data may be shared with anyone who does not have a VA appointment. All study team personnel with access to sensitive patient data must stay current on required VA information security and privacy policy trainings.

**Data Storage Location - VINCI.** Study data stored on VINCI servers is located at the Austin Information Technology Center, [name]. The specific server where the data are stored within the VINCI environment will be chosen by VINCI personnel. The server name and location within the Austin Information Technology Center may be changed at any time at the discretion of VINCI personnel.

**Specialized Software.** All software used to access sensitive patient data, whether provided by VINCI, or developed by the study team, will run in virtual desktop sessions on VINCI servers within the Austin Information Technology Center.

**Electronic CRFs:** Puget Sound will receive electronic fillable pdf format case report forms (eCRFs). The form will have a unique RSA encryption key. eCRFs will be printed and completed for each visit manually. Information captured manually will then be entered into the fillable form. eCRFs will be saved with the following file names: Site-Subject-CRFName (examples: PUG-001-Screen, PUG-001-AE). The completed eCRFs will be sent via VA email with PKI encryption to the data coordinator ([name]) at the VA Portland within 7 days of the visit. The site will receive a confirmation email from the data coordinator who will perform data accuracy and verification checks and enter the information into the Main database described above.

**OHSU Statistician.** The majority of the analysis will occur at OHSU by Biostatistician, who is listed as a study team member on this study. The dataset will be deidentified. All 18 HIPPA identifiers will be removed from the dataset and age > 90 will be aggregated. Verification of the coded data set creation and the absence of the identifiers will be created and retained in the study files. The research coordinator will be responsible for creating the dataset. The dataset will be password protected and transferred using OHSU'S FIPS compliant secure file transfer system (securex.ohsu.edu).

**OHSU FOG Lab:** The FOG Lab at OHSU specializes in gait and balance. For analysis coded sensor data will be uploaded to Mobility Exchange (located on OHSU secure server: smb:\neurodev.ohsu.edu\data); it is a clinical data management system to facilitate the secure collection, storage, and analysis of Mobility Lab (ML) data collected across multiple sites and/or institutions. MX was designed from the bottom up with HIPAA compliance as a requirement, including: 1) Secure login, 2) User based access privileges, 3) Encrypted data uploads over HTTPS/SSL, and 4) Audit trails for added/edited data. An instance of the MX server has been set up at OHSU, in accordance with OHSU's Advanced Computing Center's (ACC) standards for maintenance, backups, and security. Access to this server from outside OHSU's firewall has been established, to enable the collection of data from outside sites. Access to the MX server is only available to users who have been explicitly registered on the server by the server administrator. Once an ML instance has been associated with the MX server, only registered users can use the ML system for data collection and upload their data to MX. All communication between ML and MX is done over an encrypted protocol (HTTPS/SSL). The lab will receive coded, limited dataset that includes inertial sensor data. The lab will receive data after every visit. The research coordinator will be responsible for uploading. The statistician will be added to the OHSU side of the study when assigned by the lab.

#### *Data Repository.*

**Contact Information:** Identifiable data collected under the VA portion of this protocol will be contributed to [name] Repository, part of the Neurological Disorders Repository

(MIRB #3129). The NDR Contact Information Source document will be completed. This includes collecting name, telephone number, year of birth, neurological diagnosis, address, and any information the participant would like to volunteer about their study preferences. This data will not be coded, as it is being retained for recruitment purposes. Subjects' consent must be obtained before adding their data to the repository; subjects may decline data banking in this repository and still participate in this study. Data will be kept in \\R01PORHSM03\Services\Research\PADRECC\PAD\_Quinn\_NDR\_3129\Data.

**Data and specimens:** Post data entry and verification, data and specimens (blood) will be coded and transferred to the *Neurological Disorder Repository* operated by [name] (MIRB # 3129). This repository is maintained at the Portland VA Health Care System. Verification of the coded data set creation and the absence of the identifiers will be created and retained in the study files. The research coordinator will be responsible for the creation and verification process. The key to the code will be maintained by the study and will not be released to the repository. The repository portion of this study is optional.

#### *Data Sharing Plan (IPD):*

Individual participant data be available (including data dictionaries). Individual participant data that underlie the results reported the resultant article, after deidentification (text, tables, figures, and appendices). In addition to data, the study protocol and the informed consent form (ICF) will be provided. Data will be available beginning 6 months and ending 2 years following article publication. Data will be shared with Investigators whose proposed use of the data has been approved by an independent review committee ("learned intermediary") identified for this purpose. Data will be released to achieve aims in the approved proposal or for individual participant data meta-analysis. Proposals may be submitted up to 24 months following article publication. After 24 months the data will be available in our VA'S data repository but without investigator support other than deposited metadata. Information regarding submitting proposals and accessing data may be found at (<https://www.parkinsons.va.gov/northwest/>)

**Blood Samples.** Blood samples collected during the screening and day-long visit for cardiovascular risk calculation, storage in a repository, levodopa levels (LD), and pERK1/2 analysis. At the screening visit (or at 08:00 am on the day-long visit for the VA Puget Sound participants), approximately 1 mL of blood will be drawn by either the VA phlebotomist or an OCTRI research nurse after 12-18 hours fasting. This blood will be processed by the VA Core lab for a complete metabolic panel. Total cholesterol, HDL-C, systolic blood pressure will be used to calculate the FRS.

At 11:00 am during the day-long visit, approximately 26 mL (5 teaspoons) of whole blood will be drawn. Blood will be placed carried by the research coordinator/assistant directly to the Portland VA where the processing will occur.

**Plasma.** The samples will be centrifuged to separate plasma. Plasma will be retained (per participant's specimen repository options) in the Neurologic Disorders Repository (NDR; MIRB # 3129). 3mL of plasma will be frozen and stored for levodopa level analysis by the Pharmacokinetics Core at OHSU. Samples will be stored in a freezer located in [name] Lab at the VAPORHCS. The lab is in building 103 Room E143. Each sample will be coded with the patient's identifier, month and year of collection, and the PI's name and the study number (See Figure J). Samples will be batch processed at the Flow cytometry Shared Resource (FCSR) at OHSU. All batch samples will be hand carried to OHSU by the research coordinator. The flow cytometry core lab at OHSU will provide processing services for the pERK1/2 (extracellular signal-regulated kinase) assays. In particular, the phosho-protein analysis for the

Anti-ERK1/2. Batch analysis of the buffy coat (pERK) and levodopa levels will occur after every 30 samples. The OHSU FCSR has operated as a core resource for OHSU researchers and the Knight Cancer Institute members since 1996 and the Oregon Stem Cell Center since 2005. It provides advanced flow cytometry instrumentation, technical expertise, and technical services. The FCSR provides data analysis, data interpretation, experiment design, and routine operation to researchers.

STAT-001 12/2018 [name] e17302 pERK Buffy Coat 01	STAT-001 12/2018 [name] NDR 3129 PLASMA 01	STAT-001 12/2018 [name] 3869 Acc # 9999999	STAT-001 12/2018 [name] e17302 LD PLASMA 01
--	---	---	--

Figure J. Blood tube label examples.

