Additionally, pERK1/2 levels will be examined. Initial analysis will examine the relationship between severity of dyskinesia (with the AUC of the RMSV) and pERK1/2 levels using correlations. Further analysis will examine if pERK1/2 levels vary by cohort using ANOVAs and multiple regression techniques. Assessment of confounders of the relationship between pERK1/2 and dyskinesia severity will be examined.

**Sample Size:** Based on results of a validation study of dyskinesia scales [35], using a one-way ANOVA to examine the difference in part 3, impairment, of the Unified Dyskinesia Rating Scale (UDysRS) between the three pairwise comparisons, 37 participants are needed in each group to detect a moderate effect size ( $f=0.30$ , at least one group difference of 3.75 points) with a significance of 0.05 and power of 0.80. Pairwise comparison of statin before levodopa versus no statin will receive priority. To account for drop outs, an additional 3 participants will be included in each of the groups. Additional 10 will be included for screen failures (total 130). Total enrollment will be 40 per group, 120 total. See Table 5 for estimated recruitment goals.

*Table 5. Estimated Recruitment Totals per Site*

	VAPORHCS	VAPUGHCS	OHSU	Total
Recruitment	60	28	32	120

*Figure 1. Recruitment Goals over time*

Subjects were described previously and in the first cohort will be those who had been on a statin first and remained on it while they were initiated on LD. The second cohort will be those who started a statin AFTER beginning LD. The third cohort will be subjects with no history of statin intake. Matching will occur based on gender, severity of disease based on a PD rating scale, and LD dose

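### pERK1/2 is assayed in about four sequential batches, but no batch term is prespecified for the Aim 3 correlation or the pERK cohort comparison

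*Combined protocol and SAP*

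**What the plan says.** The laboratory plan is in the Plasma paragraph, under Data Sharing Plan (IPD): "Batch analysis of the buffy coat (pERK) and levodopa levels will occur after every 30 samples". Under Sample Size, "Total enrollment will be 40 per group, 120 total", so full enrolment gives four runs.

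The pERK analysis is in the Data Analysis section. It begins with an unadjusted association: "Initial analysis will examine the relationship between severity of dyskinesia (with the AUC of the RMSV) and pERK1/2 levels using correlations". It continues: "Further analysis will examine if pERK1/2 levels vary by cohort using ANOVAs and multiple regression techniques". A look at confounding of the relation between pERK and dyskinesia is also planned, but no variable is named. The covariate list for the main regression is open-ended, and every item on it is clinical.

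No section mentions assay batch or run as a model term, bridging or control samples, or balancing of cohorts across runs. Two other places matter. Under pERK1/2 Levels, the readout is expressed relative to ERK. Under Cohort Generation, patients are approached in the order in which they attend clinic.

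**The concern.** Readings from separate flow-cytometry runs can differ in level for technical reasons. If the runs are pooled without a batch term, that difference enters the analysis in two ways.

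- **Correlation.** Batch variation unrelated to dyskinesia adds noise to pERK, which pulls the correlation toward zero and costs power.
- **Cohort comparison.** If the cohort mix changes from run to run, differences between runs become differences between cohorts. If the mix is constant, they only inflate the residual.

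A change in mix is plausible. Recruitment follows clinic attendance, and the feasibility counts in Preliminary Studies are very unequal: 181 with a statin before levodopa, 296 after, and nearly 900 with none. The protocol versions also run from 2018 to 2022, so the runs may be far apart in time.

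Aim 3 rests entirely on pERK. The section on importance of knowledge also relies on the biomarker to keep the study valuable if statins prove ineffective.

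**Working it through.** **The plan's own figure.** Sample Size says "37 participants are needed in each group to detect a moderate effect size", "with a significance of 0.05 and power of 0.80", for f = 0.30. For a one-way ANOVA with three groups, power comes from the noncentral F distribution with noncentrality f² × N. At 37 per group this is 0.09 × 111 = 9.99 and power is 0.8035. At 36 per group power is 0.7916. The figure of 37 is reproduced. It refers to UDysRS part 3 ("at least one group difference of 3.75 points"), and the documents state no effect size or power for pERK.

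**Inputs for the check**
- From the documents: 120 subjects in batches of 30, so 120/30 = 4 batches; 40 per cohort; 37 × 3 = 111 evaluable, since "an additional 3 participants will be included in each of the groups" for drop-outs.
- Assumed: true within-batch r = 0.30, and batch variance v as a fraction of within-batch variance (0.10, 0.25, 0.50, 1.00). Batch then explains v/(1+v) of total pERK variance: 9%, 20%, 33%, 50%. Batch is taken as unrelated to dyskinesia.

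**Step 1, correlation.** Expected r without adjustment is 0.30/√(1+v). Two-sided 5% power uses Fisher's z: Φ(atanh(r)·√(n−3) − 1.96), with n = 111 and √108 = 10.39. The opposite tail is negligible.

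| v | expected r | power |
|---|---|---|
| 0 | 0.300 | 0.896 |
| 0.10 | 0.286 | 0.86 |
| 0.25 | 0.268 | 0.82 |
| 0.50 | 0.245 | 0.74 |
| 1.00 | 0.212 | 0.61 |

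With batch as a four-level factor, r stays at 0.30 and three degrees of freedom are lost: atanh(0.30)·√(111−3−3) = 0.3095 × 10.25 = 3.17, and Φ(3.17 − 1.96) = 0.887. That is also the power if no batch effect exists, so the price of the term is 0.896 to 0.887.

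**Step 2, cohort ANOVA.** Null data were simulated with four batches of 30, 40 per cohort and no true cohort difference. Three patterns of cohort mix were used. The assumed drift has cohort A/B/C counts of 6/8/16, 8/10/12, 12/11/7 and 14/11/5 over the four batches. The drift row uses 20,000 sets per setting, and the other two use 6,000. Entries are false-positive rates at nominal 5% without a batch term.

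| cohort mix | v=0.10 | v=0.25 | v=0.50 | v=1.00 |
|---|---|---|---|---|
| drift | 0.060 | 0.072 | 0.094 | 0.120 |
| balanced | 0.040 | 0.034 | 0.024 | 0.012 |
| random arrival | 0.052 | 0.050 | 0.050 | 0.047 |

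With a batch factor the rate under this drift is 0.048 to 0.051. In a separate run of 4,000 sets, with batch explaining 10 to 30% of total variance, the batch-adjusted rate was 0.047 to 0.052 under balance and 0.050 to 0.056 under random arrival. A somewhat steeper drift in that run gave 0.069 to 0.125 unadjusted and 0.049 to 0.054 adjusted.

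**The case against.** The strongest case on the other side is that this is an omitted detail and not a wrong analysis.

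- The confounder wording and the open covariate list leave room for a batch factor without any change to the plan. This is true, but permission is not commitment. The first analysis is an unadjusted correlation, and a batch term chosen after seeing results is what prespecification should prevent.
- Expressing pERK relative to ERK may remove some shared variation, and a single core facility runs the assay. Both may reduce batch variance. Nothing in the documents shows that they remove it. A laboratory manual may specify run controls, but it is not part of these documents.
- A reader might infer that Aim 3 is attenuated as a matter of fact. The documents do not support that, because they give no batch variance. At the low end of the range the loss is minor (r from 0.30 to 0.29, power from 0.89 to 0.86), and the upper end needs batch to explain a third to a half of all pERK variance.
- A reader might also infer that the cohort test has a broken error rate. That needs batch variance and drift together. Under random arrival the test is nominal, and under balance it is conservative. The assumed drift is substantial: only about 6 to 7% of random arrival orders would be as uneven (chi-square 12.0 on 6 df). No section says that the cohorts fill at different speeds. Unequal pools make this plausible but do not establish it.

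The last two objections stand, and they limit the point to a conditional one.

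**Conclusion.** The point holds in conditional form. pERK1/2 is run in about four sequential batches, and neither stated analysis commits to a batch term. If between-batch variance is material, the correlation may be attenuated by the amounts in Step 1. The cohort test may then err in either direction, or not at all, depending on how the cohorts fall across batches. If batch or calendar time is itself related to dyskinesia, the correlation could be biased either way.

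The sizes rest on an assumed r of 0.30, assumed batch variances and an assumed drift. The absence of a batch term and the small cost of adding one do not rest on those assumptions.

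The consequence is confined to Aim 3. The Overview ranks the ERK1/2 correlation as tertiary, although Data Analysis groups pERK1/2 with secondary outcomes. The primary UDysRS comparison is untouched. This is a worthwhile, inexpensive improvement and not a flaw in the main result.

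**What to change.** In the pERK paragraph of Data Analysis, make two changes:

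1. Replace the simple correlation with a partial correlation, or a regression of pERK1/2 on AUC RMSV, with assay batch as a fixed factor.
2. Include assay batch as a fixed factor in the pERK cohort ANOVA and regression.

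The cost is one or two sentences in the plan and 3 degrees of freedom, with no new samples or visits. The run in which each sample was assayed must be recorded in the dataset.

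Recomposing batches to balance the cohorts is not recommended. It conflicts with running the assay after every 30 samples and would mean holding some samples longer, which adds storage-time variation.

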## Human Subjects.

### *Risks to Subjects*

#### **Human Subjects Involvement and Characteristics**

*Involvement of human subjects:* Veterans with PD will be asked to attend 1 screening visit at the VAPORHCS, VAPUGHCS, or OHSU and 1 visit in the outpatient unit of OCTRI located at OHSU.

*Subject population:* 120 subjects veterans and non-veterans will be consented and enrolled. Subjects with probable idiopathic Parkinson Disease, a clinically-based diagnosis based upon history and a physical examination that does not suggest an alternate diagnosis (UK Brain Bank Criterion). Subjects will be diagnosed with PD after the age of 49. Subjects will not be demented, defined by a Montreal Cognitive Assessment of <18, psychotic (hallucinations or delusions by history), or using medications that block dopamine receptors, or have been postulated to worsen parkinsonism or affect dyskinesia. Any unstable medical conditions will also be cause for exclusion. Current substance abuse is an exclusionary criterion. Other classes of PD medications are allowed.

*Subject compensation:* Participants will be compensated \$50.00 for completion of the all-day visit, and \$10.00 for the screening visit. Total compensation of \$60.00 for completion of the study visits. This compensation is to pay for transportation, food, and potentially time away from work. This compensation is commensurate with previous protocols conducted by the PI involving full-day visits.

Veterans recruited by the Puget Sound site will need to travel to Portland for the day IV levodopa infusion. Travel costs (including Amtrak train from Seattle, Hotel in downtown Portland, and cab fare to and from Oregon Health & Science University) will be reimbursed.

